## 1.0 Background

Extinction describes discontinuation of reinforcement that results in decreases in a measurable dimension of behavior (e.g., frequency, duration; Cooper et al., 2020). **Bursts are the most common collateral effect of extinction** (Ducharme & Van Houten, 1994) and are characterized by a temporary increase in behavior, relative to baseline (see Figure 1; Alessandri et al., 1990; Iwata et al., 1990; Laws et al., 1971; Lerman & Iwata, 1995). Although the general prevalence of bursts can be estimated (e.g., Lerman & Iwata), no method exists to control their occurrence.

[figure not shown]
Notwithstanding, control is valuable. **Treatments of challenging behavior are less effective when they do not include extinction** (Fisher, et al., 1993; Hagopian et al., 1998; Mazaleski et al., 1993; Rooker et al., 2013; & Zarcone et al., 1994). However, when problem behavior is dangerous, practitioners may not risk increasing its rate or intensity. Thus, extinction is often omitted in the service of safety (and at the cost of efficacy). **If we understood why bursts occurred, we could proactively work to mitigate their occurrence; thereby making extinction a viable treatment option in more settings.**

**Figure 2: Value estimates derived from demand curve analysis**

effects of stimuli; however, can be relative and volatile (Baum, 1974; Michael, 1975; Hineline, 1984; Perone, 2003). Simply put, different reinforcers support different magnitudes/ qualities of responding (e.g., Hodos, 1961). Thus, although someone might be willing to share a thought for a penny, they are unlikely to build a house for one. This “not all reinforcers are created equal” epiphany has inspired scientists to study “value” (i.e., variables which alter the degree to which specified consequences support specified outputs). **As bursts are likely a product of baseline reinforcement parameters, consideration of value is essential to understanding the phenomenon.**

Concepts in consumer-demand theory (Bickel et al., 2000) may prove useful to this analysis. Specifically, in behavioral economics, **demand** describes the quantity of a given commodity (e.g., 10 gallons of gas) an individual consumes at an established price (e.g., \$2/gallon). When demand is *inelastic*, consumers work harder (or pay more) as prices increase, to maintain baseline levels of consumption. For example, motorists are unlikely to purchase less gas if price increases by \$0.05. However, demand can become *elastic*. That is, as price increases, consumption begins to share an inverse relation with those increases. In the previous example, motorists may eventually purchase less gas and drive to fewer places if the price of a gallon were to increase by \$5.00. The shift in demand from inelastic to elastic is a point of interest because it quantifies commodity (reinforcer) value and helps identify optimal prices. **The optimal price, or**

**Figure 1: Example of burst**

[figure not shown]
Available evidence suggests baseline reinforcement parameters influence responding (i.e., behavior) during extinction (Aiken, 1957; Holton, 1961; Nevin et al., 1990; Perin, 1942; Siegel & Foshee, 1953; Young, 1966). The reinforcing

$P_{max}$ , is the price that supports maximum consumer spending (or Omax, see top left panel of Figure 2). Prices below  $P_{max}$  undervalue commodities because consumers *would* spend more than required. Similarly, prices above  $P_{max}$  are suboptimal because these price points decrease the value of the commodity and consumers won't spend as much to obtain it as they would if pricing had been more reasonable. For reasons expanded upon below, the concept of  $P_{max}$  may prove useful for understanding bursts.

Related, **demand** (defined above) can be used to quantify *temporary* shifts in value at a specified price because the value of *additional* consumption is decreased as consumption approximates demand. Individuals stop "paying" for reinforcers after they have crossed this threshold (see bottom panels of Figure 2). Laraway et al. (2003) accounts for this effect by distinguishing antecedent events (e.g., deprivation) that temporarily increase value of consequences (e.g. access to food) from other antecedent events (e.g., satiation) that work in the opposite direction and deplete value. The former is an establishing operation (EO) and the latter is an abolishing operation (AO). Using these terms, one might say the value of *additional* consumption is abolished (decreased) the closer consumption gets to demand. By contrast, the value of *additional* consumption is established (increased) when little/no consumption has occurred.

Generally,  $P_{max}$  and demand have not been considered in published treatments of bursts. However, as bursts are likely a product of baseline reinforcement conditions, and because value can fluctuate according to molar (i.e., unit price) and molecular (i.e., satiation/deprivation) variables (right panel, Figure 2), consumer-demand theory may provide a useful framework from which to formulate and test hypotheses relevant to bursts. For example, **it is possible that bursts are a product of baseline schedules of reinforcement (i.e., "unit prices"), relative to  $P_{max}$ .** Specifically, if baseline prices (i.e., number of responses required to obtain a reinforcer) are a bargain because they are "cheaper" than  $P_{max}$ , consumers may be more inclined to increase output to a value that approximates Omax during extinction (a pattern typified by "bursts"). Likewise, if baseline prices are "more expensive" than  $P_{max}$ , then output has already been diminished and bursts may be less likely. **It is also possible that bursts are a product of the timing of extinction.** Specifically, if, prior to extinction, consumption has approximated demand (thereby abolishing additional consumption as a reinforcer), responding during extinction may be less than if the inverse were true. **Finally, it is possible that price (relative to  $P_{max}$ ) and timing (i.e., pre-extinction consumption relative to demand) interact.**

## 2.0 Rationale and Specific Aims

**Figure 3: Predictions**

**The Goal** of this application is to identify mechanisms responsible for bursts, and to facilitate strategic extensions toward discovery for treatments of challenging behavior. To accomplish this, we present two

related but distinct objectives. **Objective 1** entails identification of an efficient, accurate, and reliable assessment of  $P_{max}$ . **AIM 1: Evaluate correspondence between  $P_{max}$  values derived from assessments of varying efficiency. *H1: Progressive ratio (PR) reinforcer analysis (more efficient) will produce estimates which align with values obtained by progressive fixed-ratio reinforcer analysis (PFRA; less efficient).*** **Objective 2** entails determining the degree to which relative price and the timing of

extinction interact to increase or abate responding during extinction (thereby highlighting mechanisms of control). **AIM 2: Evaluate utility of manipulating baseline parameters for controlling bursts when variables are set according to demand and Pmax.** **H2:** Peak response magnitude during extinction will decrease as unit price increases. Further, *baseline will moderate bursts in one of three distinct ways*. **First**, only unit price, relative to Pmax, will influence peak-response magnitude. **Second**, only timing of extinction (i.e., proximity of baseline consumption to demand threshold) will influence peak-response magnitude. **Third**, unit price relative to Pmax, and consumption relative to demand, interact to influence peak-response magnitude during extinction.

### 3.0 Inclusion/Exclusion Criteria

#### Inclusion Criteria

- (a) Biological age of 18 years or older
- (b) IDD diagnosis
- (c) Ability to correctly manipulate all items used in the study
- (d) Consent/assent prior to and throughout the study

#### Exclusion Criteria

- (a) Biological age of 17 years or younger
- (b) No disability
- (c) Cannot correctly manipulate all items used in the study
- (d) Does not consent (or assent) to participate

**Enrollment & Randomization.** Because this is a low-risk trial with a limited budget, the PI ([name]) will be responsible for carrying out randomization procedures and for monitoring data. Enrollment and randomization procedures will entail:

1. Enrolling participants in batches of 10
2. Matching two blocks of four participants based on similarity in pertinent baseline assessment scores (i.e., progressive-ratio reinforcer analysis), and relegate participants with outlier scores to block participation with the next batch of enrolled participants.
3. Using the randomization and sorting functions of Microsoft Excel, we will randomly assign each member of each block within each batch of participants to one of four experimental conditions (i.e., cheap+EO, cheap+AO, expensive+EO, expensive+AO).

**Registration.** We have initiated the study registration process with clinicaltrials.gov.

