## 5.0 Study Procedures

We will schedule 1 to 4 appointments per week with each participant across a 1-month period. All participants will complete the same progression: (1) interview (i.e., set appointments, identify programmed reinforcers and target-responses), (2) target-response training, (3) PRA, (4) PFRA, (5) extinction challenge.

**Experimental Design.** Following completion of a small battery of intake assessments (listed above), we will evaluate between-groups differences in peak-response magnitudes during a single exposure to extinction using a 2x2 factorial, crossed, and randomized matched blocks design, employing batched randomization logic. Specifically, we will recruit participants in batches of ten and will match two tetrads according to similarity in PRA results (described below). The two participants not assigned to a group will be matched to subsequent tetrads. Or, (if recruited in the final batch), paid for their time and discharged. To assign members of each tetrad to one of four experimental groups (i.e., cheap EO, cheap AO, expensive EO, expensive AO), we will use randomization functions of appropriate computer software (e.g., Microsoft Excel).

**Settings, Participants, Consent, & Compensation.** Recruitment will occur across six primary research sites. Best Buddies Tennessee, The Metro Parks DisABILITIES program, Habilative and Training Services (HATS), Down Syndrome Association of Middle Tennessee (DSAMT) Next Steps at Vanderbilt, Friends Life Community, and MillarRich. We will have offered letters of support. Across the life of the study, we will recruit 80 adults in batches of 10. We do not anticipate biological variables (e.g., sex) to impact study outcomes. Inclusion criteria call for participants: (a) to be older than 18 (we exclude children to obey labor laws), (b) to have a developmental disability (unconstrained to specific diagnoses. We chose to work with a heterogeneous sample to increase the generality of our findings), (c) to correctly manipulate all study items, and (d) to consent prior to and throughout the study. If participants cannot legally consent, we will obtain consent from guardians and will assess assent throughout the study (i.e., at the beginning of every session). **Importantly, pilot-study participants consented to all procedures on an ongoing basis.** We will pay participants with gift cards, on a schedule commensurate with minimum wage (\$7.25/hr).

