### **8.0 Statistical Considerations**

**Power Analysis.** Power analysis and sample size calculations were conducted using G\*power software. Since our study represents a novel contribution, we cannot rely on previous literature to estimate the population value of R-squared or the appropriate effect size. However, our pilot suggests the effect size will not be small. Thus, we calculated sample size based on a benchmark value for Cohen's  $f^2$  of 0.15 that corresponds to a medium effect size for R-squared (Cohen, 1988). To achieve 80% power in a regression model with three predictors and  $\alpha = .05$ , 77 participants are required. With this sample, the power to find any one of the three predicted effects (given medium effect size) is 88%. As participants will be equally distributed across four groups, we budgeted effort for 80 participants. Under our most conservative study assumptions, AIMS 1 & 2 are adequately powered.

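### The plan counts 80 both as recruited and as randomised, but its batch rule taken literally randomises 64, which lowers power for the overall test from the stated 80% to about 71%.

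*Combined protocol and SAP*

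**What the plan says.** **Recruitment.** Section 5.0 (Settings, Participants, Consent, & Compensation) states: "Across the life of the study, we will recruit 80 adults in batches of 10". That is eight batches.

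**Allocation.** Step 2 of the procedure in Section 4.0 is "Matching two blocks of four participants based on similarity in pertinent baseline assessment scores", with participants whose scores are outlying held for the next batch. Section 5.0 (Experimental Design) repeats two tetrads per batch of ten. It says that the two people without a group are matched into later tetrads or, "if recruited in the final batch), paid for their time and discharged". Each tetrad supplies one person to each of the four conditions.

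**Sample size.** Section 8.0, which largely repeats the Power Analysis paragraph of Section 5.0, says "we calculated sample size based on a benchmark value for Cohen's" f² of 0.15. For 80% power with three predictors and alpha 0.05, "77 participants are required". Because the groups are to be equal in size, "we budgeted effort for 80 participants". The same text also gives a power of 88% for any single effect.

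**Withdrawal.** Section 7.0 lets participants stop at any time. The sample-size text makes no allowance for this, or for people discharged unassigned.

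**The concern.** The number 80 does two jobs. In Section 5.0 it is the number recruited. In the power text it is the number divided equally over four groups, that is, 20 per group. The two agree only if every recruit is randomised, whereas the allocation rule places eight of every ten and expects to send some people home at the end.

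No section gives a target for the number randomised or says whether carried-over participants make an additional tetrad or take places in the usual two. If they only take places, each one displaces someone else and the total does not rise. The sample size and its power would then be figures that the trial's own procedure does not produce. The choice between readings would fall to the principal investigator, who carries out the randomisation, while the study is running.

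**Working it through.** **Inputs.** 80 recruits, batches of ten (Section 5.0); two blocks of four per batch (Sections 4.0 and 5.0); carry-over and final-batch discharge (Section 5.0); f² = 0.15, three predictors, alpha 0.05, required N of 77 (Section 8.0).

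**Step 1: reproduce the plan's figure.** The overall test that all three coefficients are zero has 3 and N − 4 degrees of freedom and noncentrality λ = f² × N. Its power is the probability that a noncentral F variable exceeds the 95th percentile of the central F. At N = 77, λ = 0.15 × 77 = 11.55 with 3 and 73 degrees of freedom, and power is 80.2%. At N = 76 it is 79.6%. The smallest N reaching 80% is therefore 77, as the plan states. This also shows that the 77 is the size for the overall test.

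**Step 2: count those randomised.** There are 80 / 10 = 8 batches.

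- *Two tetrads in every batch.* 8 × (2 × 4) = 64. The unassigned pool grows by two per batch, and 16 people are left at the end.
- *Carry-overs may form extra tetrads; two final-batch participants are discharged.* At most 80 − 2 = 78 remain. Tetrads need a multiple of four, so at most 19 × 4 = 76.
- *Carry-overs form a third tetrad whenever twelve people are available.* Batch 1 has a pool of 10: 8 assigned, 2 carried. Batch 2 has a pool of 12: 12 assigned, none carried. The pattern repeats, so each pair of batches randomises 20, and 4 × 20 = 80. The eighth batch has a pool of 12 and nobody is left to discharge.

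**Step 3: power at each count.** The single-coefficient column uses a two-sided test with 1 and N − 4 degrees of freedom and gives f² = 0.15 to that one coefficient.

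| Reading | N | λ = 0.15N | Overall test | Single coefficient |
|---|---|---|---|---|
| Two tetrads per batch | 64 | 9.60 | 71.1% | 86.2% |
| Extra tetrads, two discharged | 76 | 11.40 | 79.6% | 91.5% |
| Plan's required size | 77 | 11.55 | 80.2% | 91.8% |
| Third tetrad in alternate batches | 80 | 12.00 | 81.9% | 92.8% |

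The plan's 88% for a single effect was not reproduced: this calculation gives 91.8% at 77. That is a separate matter and does not touch the 80% and 77 pair.

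**Step 4: margin for losses.** With 80 randomised, 80 − 77 = 3, so a fourth loss takes the analysed number below 77. The documents give no withdrawal rate. Under assumed losses of 5%, 10%, 15% and 20%, the 80 become 76, 72, 68 and 64, with overall power of 79.6%, 77.0%, 74.2% and 71.1%.

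**The case against.** The best reply is that the plan can be read so that it works. Section 5.0 promises that unassigned people will be matched to later tetrads, and the discharge clause can be taken as a contingency for anyone who happens to be left. On that reading all 80 are randomised, which agrees with the equal groups in the power text. The other two readings fit Section 5.0 imperfectly. At 64, sixteen people are unassigned, and most of them have no stated outcome because discharge covers only the final batch. At 76, four are unassigned although the text speaks of two.

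This stands in part. A reader might infer that the rules can never randomise more than 76, so that 77 is out of reach. The documents do not support that: full carry-over reaches 80, and 76 itself already needs more than two tetrads in some batches, so the two-tetrad wording cannot exclude 80 while admitting 76. But the 80 reading needs three tetrads where both sections say two, and it leaves the discharge clause with nothing to do. No reading satisfies every sentence.

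It is also fair that 76 costs only 0.6 percentage points against 77, and that the three research questions concern individual effects. A reader might infer that those individual tests are underpowered at 64. At the planned f² they are not: single-coefficient power is 86.2%.

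**Conclusion.** The inconsistency is real. Depending on the reading, between 64 and 80 participants are randomised, and the literal rule gives 64. Power for the overall three-predictor test is then 71.1%, about 9 points below the 80.2% at the plan's own 77. The 76 reading is immaterial, and the 80 reading meets the target but is not written down. The material shortfall therefore depends on the literal two-tetrad rule and is confined to the overall test.

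These figures take the plan's f² of 0.15, alpha of 0.05 and three predictors as given, with exactly 80 recruited and no losses. Withdrawal would reduce the analysed number under every reading, but its extent is unknown, so the power figures in Step 4 of the working illustrate and do not predict. With no loss allowance and a margin of three at best, the claim that both aims are adequately powered under the most conservative assumptions is not supported for the overall test.

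**What to change.** The text is wrong as written and should be corrected in two places.

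1. **Sections 4.0 and 5.0 (Experimental Design).** Replace two blocks of four per batch with as many blocks of four as can be formed from all participants not yet assigned. State the target as 20 tetrads, 80 randomised, separately from the 80 recruited. Keep the discharge clause only for anyone still unassigned after the last batch.
2. **Section 5.0 (Power Analysis) and Section 8.0.** Give power at the number randomised (81.9% for the overall test at 80), and say that more than three losses from 80 takes the analysed number below 77. Any withdrawal rate used should be labelled an assumption and shown as a range.

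If the sponsor prefers to keep two tetrads per batch, the size should be restated as 64 and the overall power as about 71%. Randomising 80 under that rule would take ten batches, or 100 recruits (10 × 8 = 80).

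The cost of the main change is wording and a restated power figure, with no extra recruitment to reach 80 randomised. The downside is looser matching when held-over participants with outlying scores enter a third tetrad. The change does not protect against withdrawal; holding 80% power after more than three losses would need further recruitment.

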## 5.0 Study Procedures

We will schedule 1 to 4 appointments per week with each participant across a 1-month period. All participants will complete the same progression: (1) interview (i.e., set appointments, identify programmed reinforcers and target-responses), (2) target-response training, (3) PRA, (4) PFRA, (5) extinction challenge.

**Experimental Design.** Following completion of a small battery of intake assessments (listed above), we will evaluate between-groups differences in peak-response magnitudes during a single exposure to extinction using a 2x2 factorial, crossed, and randomized matched blocks design, employing batched randomization logic. Specifically, we will recruit participants in batches of ten and will match two tetrads according to similarity in PRA results (described below). The two participants not assigned to a group will be matched to subsequent tetrads. Or, (if recruited in the final batch), paid for their time and discharged. To assign members of each tetrad to one of four experimental groups (i.e., cheap EO, cheap AO, expensive EO, expensive AO), we will use randomization functions of appropriate computer software (e.g., Microsoft Excel).

**Settings, Participants, Consent, & Compensation.** Recruitment will occur across six primary research sites. Best Buddies Tennessee, The Metro Parks DisABILITIES program, Habilative and Training Services (HATS), Down Syndrome Association of Middle Tennessee (DSAMT) Next Steps at Vanderbilt, Friends Life Community, and MillarRich. We will have offered letters of support. Across the life of the study, we will recruit 80 adults in batches of 10. We do not anticipate biological variables (e.g., sex) to impact study outcomes. Inclusion criteria call for participants: (a) to be older than 18 (we exclude children to obey labor laws), (b) to have a developmental disability (unconstrained to specific diagnoses. We chose to work with a heterogeneous sample to increase the generality of our findings), (c) to correctly manipulate all study items, and (d) to consent prior to and throughout the study. If participants cannot legally consent, we will obtain consent from guardians and will assess assent throughout the study (i.e., at the beginning of every session). **Importantly, pilot-study participants consented to all procedures on an ongoing basis.** We will pay participants with gift cards, on a schedule commensurate with minimum wage (\$7.25/hr).

**Materials and Target Response.** For each participant, we will individualize and define (a) a target response with a corresponding apparatus, (b) a preferred edible item or sound manipulation ([name] et al., *in press*), and (c) a moderate- to low-preferred tangible item. All target responses will involve a two-step manipulation and restoration. The final step of each target response (i.e., restoration) will automatically set up another opportunity to complete the task (e.g., fold/unfold a hand towel).

**Dependent Variables, Procedural Fidelity, and Interobserver Reliability.** We will collect continuous timed-event measures of the frequency of target responding and reinforcer delivery, latency from session onset to delivery of programmed reinforcers, and overall session duration. Derivative measures appropriate to each analysis will serve as our dependent variables and will include breakpoint (i.e., the schedule of the last obtained reinforcer prior to response cessation [PRA]), demand (i.e., the number of reinforcers obtained prior to response cessation [PFRA]), Pmax (defined above [PRA & PFRA]), and peak response rate during extinction (Figure 1), depicted as a proportion of baseline (e.g., Figure 4). We will monitor fidelity, and a second trained observer will collect reliability data on all dependent variables across no fewer than 30% of sessions.

**General Appointment Protocol.** To minimize unintended coercive practice, all assessment-related activities will be framed as a choice. Specifically, facilitators will initiate appointments with a 5-min casual conversation. Prior to each session, facilitators will display the apparatus for target response and a low-preferred alternative activity and will say, “We are going to start a session, now. This just means I’m going to give you an opportunity to earn (reinforcer). During sessions I cannot talk to you. That’s just a rule I have to follow. It doesn’t mean I don’t want to talk or that I’m not happy. If you want (reinforcer) after the session starts, you can work on (target response). If you don’t want (reinforcer), or would rather talk to me, you only need to stop (target response) for one minute. You can also just say, ‘I’m done’. While you wait, you can (alternative activity) if you like.” All appointments will terminate the moment a participant indicates they would like it to end.

**Response Training.** Will entail a forced-choice exposure and 10 opportunities to independently earn reinforcers (1/response). If independence is not achieved, we will target different responses and reinforcers.

**Progressive Ratio Reinforcer Analysis (PRA).** Begins with free-access, followed by three PRAs interspersed with controls. Control will occur prior to PRA. To avoid satiation, only one PRA will be conducted per appointment. Thus, including free access, this assessment requires four appointments. **Free access.** Carefully measured units of the reinforcer will be delivered freely, independent of target responding. Participants will be informed they can consume (e.g., eat, listen to) reinforcers at will, and that reinforcers will be replaced (when relevant) as they are consumed. Sessions end when no reinforcers are consumed for one minute. **Control.** Facilitators will place the target-response apparatus in front of participants and indicate that responding will not result in reinforcement. Sessions end following 1 min without responding. **PRA.** Facilitators will indicate that responding results in reinforcement, but that more work will be required as time passes. Following every other reinforcer delivery, price will increase by three responses (i.e., FR1, FR4, FR7, etc.).

[figure not shown]
**Progressive Fixed-Ratio Reinforcer Analysis (PRFA).** Will be similar to PRA with a few exceptions. First, no control condition. Next, within-session schedules are fixed. That is, requirements increase by 3 across sessions, rather than across reinforcers (this allows us to establish demand at each schedule). To control for satiation, we’ll conduct one PRFA session per appointment (session ends following 1 min without responding; or after 1 hour). The assessment ends after aggregate responses for one session fall below those of previous sessions (thus avoiding premature exposure to extinction). During our pilot study, this assessment was completed in six or fewer appointments, each ranging from 5 to 27 min.

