
**Data Analysis Plan.** We will evaluate between-groups differences in peak magnitudes of responding during a single exposure to extinction using a 2x2 factorial, crossed, and randomized matched blocks design, employing batched randomization logic. First, we will calculate *observed* and *analytic* Pmax values (Gilroy et al., 2019) generated from logarithmically transformed PRFA outcomes to evaluate accuracy, reliability, and correspondence of Pmax estimates generated from PRA calculations (Reed et al., 2009). PRFA-PRA Pmax comparisons will be performed for each of the 160 PRA/PRFA assessments. Correspondences in Pmax will be assessed using Pearson correlations. Then, we will conduct a simple linear regression to assess relations between unit price and peak response magnitudes. Then, to evaluate (a) the effect of the timing of extinction (EO/AO) on peak response magnitude, (b) the effect of relative price (cheap/expensive) on response magnitude, and (c) price by timing interaction (whether the effect of timing on peak response magnitude changes depending on price) we will conduct a multiple linear regression analysis with price and timing as dummy coded categorical predictors. We will replicate this

analysis to evaluate collateral effects on *duration* of responding during extinction (a secondary analysis we anticipate will produce a less robust but potentially meaningful outcome).

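### With the PRA always before the PFRA and only a Pearson correlation planned, Aim 1 can show that the two Pmax values move together, but not that the PRA is accurate or that a level difference is due to method

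*Combined protocol and SAP*

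**What the plan says.** The opening paragraph of Section 5.0 sets one sequence: "All participants will complete the same progression: (1) interview", and the list goes on "2) target-response training, (3) PRA, (4) PFRA, (5) extinction challenge". Nothing in the protocol counterbalances or randomises the two assessments, and no check for order or drift is planned.

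The PRA paragraph says the phase "Begins with free-access, followed by three PRAs interspersed with controls". Including free access it takes four appointments. In the controls, responding earns nothing. The PFRA follows over later appointments, has no control condition, and raises the requirement by three responses from one session to the next. In the pilot it took at most six appointments.

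Section 2.0 states H1: PRA analysis "will produce estimates which align with values obtained by progressive fixed-ratio reinforcer analysis". The Data Analysis Plan in Section 5.0 says observed and analytic PFRA Pmax values will be used "to evaluate accuracy, reliability, and correspondence of Pmax estimates generated from PRA calculations". The only statistic it names for this is: "Correspondences in Pmax will be assessed using Pearson correlations".

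**The concern.** Aim 1 uses the PFRA as the reference against which the quicker PRA is judged. Accuracy and alignment are statements about level: does the PRA give the same Pmax, or one that is systematically too high or too low? Two features of the plan stand in the way.

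- **Order.** The PFRA always comes after free access, three PRA runs and unreinforced control sessions. Practice, waning interest in the item, or the history of non-reinforcement could move the second measurement. The safeguard of one PRA or PFRA session per appointment limits satiation within an appointment, not carry-over from one assessment to the other. Because the PFRA ends once responding in a session drops below that of earlier sessions, waning interest could also end it early.
- **Statistic.** Pearson's r takes no account of level, so it would not reveal a systematic difference from either source.

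At stake is the Aim 1 conclusion. A high correlation could be reported as showing that the PRA is accurate when it shows only that participants keep their relative positions. A level difference, if someone computed it, could be put down to the PRA when it partly reflects being assessed second.

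**Working it through.** **The plan's own figures.** The plan states: "PRFA-PRA Pmax comparisons will be performed for each of the 160 PRA/PRFA assessments". This fits 80 participants × 2 methods = 160 assessments, that is, 80 pairs. The power calculation (77 required, 80 budgeted) concerns the three-predictor regression. It reproduces: power is 80.2% at N = 77 with f² = 0.15 and α = 0.05. It does not bear on agreement in Aim 1, for which the documents give no figure.

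**Can method and order be separated?** Model Pmax as intercept + method + order. Under the fixed sequence the method and order columns are identical, so the design matrix has rank 2 for 3 parameters. With a 40/40 split of orders it has rank 3, provided there is no carry-over specific to one sequence.

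**What does Pearson's r show?** Assume equal SDs of 1, correlation ρ, and a shift δ common to everyone on the second assessment. Then r = ρ whatever δ is, while Lin's concordance coefficient is CCC = 2ρ / (2 + δ²).

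| δ (SD) | r | CCC, ρ = 0.70 | CCC, ρ = 0.90 |
|---|---|---|---|
| 0 | ρ | 0.70 | 0.90 |
| 0.25 | ρ | 1.4/2.0625 = 0.68 | 1.8/2.0625 = 0.87 |
| 0.5 | ρ | 1.4/2.25 = 0.62 | 1.8/2.25 = 0.80 |
| 1.0 | ρ | 1.4/3 = 0.47 | 1.8/3 = 0.60 |

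The same table applies if δ is a true method bias, or the sum of the two. An agreement statistic exposes the shift; it does not say where the shift came from.

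If the order effect varies between people with SD s, independently of Pmax, then r = ρ/√(1 + s²). For ρ = 0.70 and s = 0.25, 0.5 and 1.0 this gives 0.68, 0.63 and 0.50. The correlation is thus immune only to a uniform shift.

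**How easily would an order shift pass for a method difference?** This applies only if a paired t test were run, which the plan does not specify. Assume 80 pairs, no true method difference, and an SD of the paired difference of 3, 4.5 or 6 responses (1 to 2 schedule steps). The SE is SD/√80 = 0.34, 0.50 or 0.67. Probability of a significant difference at two-sided 5%:

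| Order shift (responses) | SD 3 | SD 4.5 | SD 6 |
|---|---|---|---|
| 0.75 | 60% | 31% | 20% |
| 1.5 | 99% | 84% | 60% |

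**What would counterbalancing remove?** Let m be the true method difference (PFRA minus PRA), d1 the shift in the PFRA when it comes second, and d2 the shift in the PRA when it comes second. The expected difference is m + d1 in one sequence and m − d2 in the other, and their average is m + (d1 − d2)/2. If d1 = d2, the bias is zero and the false-positive rate returns to 5%. If d1 = 1.5 and d2 = 0, the remaining bias is 1.5/2 = 0.75 responses, and the rates are again 60%, 31% and 20%. Asymmetry is plausible here, because only the PRA phase contains unreinforced controls.

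**The case against.** The strongest defence has four parts.

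- **The planned statistic is untouched by a common order shift.** True, and the false-positive rates above therefore describe an analysis that is not in the plan. But this is also why r cannot carry a statement about accuracy, whatever the order.
- **PRA-first is a reasonable choice.** The efficient assessment is tested in people with no PFRA history, which is arguably how it would be used, and its estimate carries no PFRA carry-over. This stands. It moves the possible contamination to the PFRA, which is the reference.
- **A uniform history protects Aim 2.** PRA scores drive the matching, and PRA and PFRA results set baseline schedules, session and appointment lengths, and the timing of extinction. Reversing the order for half the sample would mean these values were obtained in different positions. It would also send those participants from the PRA phase, with its unreinforced controls, straight to the extinction challenge. This stands, and it is why counterbalancing should not be presented as the obvious answer.
- **No order effect has been shown.** Also true: the documents neither report one nor rule one out.

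A reader might infer that the fixed order makes it impossible to judge PRA accuracy at all. The documents do not support that. Close absolute agreement would still favour the PRA unless method and order effects happened to cancel, and three PRA sessions per person permit a partial check for drift. What is lost is the ability to attribute a disagreement to method, and to exclude cancellation where there is agreement.

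**Conclusion.** The point holds in a limited form. Under the fixed sequence, a mean PRA–PFRA difference in Pmax is method plus order, and no analysis of these data can split the two. Separately, the Pearson correlation cannot support either the stated evaluation of accuracy or the H1 claim of alignment: under the assumed shifts, concordance can fall from 0.70 to 0.47 with r unchanged. That follows algebraically. The sizes of shift, the correlations and the SDs are illustrative assumptions, because the documents supply none.

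Two further inferences would go too far. The 60% to 99% rates for a 1.5-response shift are not error rates of this trial's planned analysis. Nor would counterbalancing guarantee a 5% rate, since that needs equal order effects in both sequences. The matter limits what Aim 1 may conclude; it does not undermine the randomised comparison in Aim 2.

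**What to change.** **Analysis.** In the Data Analysis Plan, alongside Pearson's r, add the paired PRA–PFRA difference in Pmax with its 95% confidence interval and limits of agreement (or a concordance coefficient), for the observed and the analytic PFRA values. State which single PRA value per participant, out of three sessions, enters the pair. With 80 pairs and the assumed SD of 3 to 6 responses, the interval would be about ±1.99 × SD/√80 = ±0.67 to ±1.34 responses, and the limits of agreement about ±1.96 × SD = ±5.9 to ±11.8 responses around the mean difference.

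**Claim, if the order stays fixed.** Limit the Aim 1 conclusion to rank correspondence plus agreement under the PRA-then-PFRA sequence. State that any level difference combines method and order. Drop the claim that PRA accuracy as such is established.

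**Cost.** A little more analysis of data already being collected, and a narrower Aim 1 claim.

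**Optional.** Counterbalance the order. The SE of the method difference (SD/√80) and the sample size are unchanged, but this removes only order effects that are equal in both sequences. Matching scores and schedule-setting values for Aim 2 would then come from different positions. Order would have to be balanced across the four groups, for example by holding it constant within tetrads, and included as a covariate. With five participants per order in a batch of ten, each order could supply one tetrad and one person carried forward, at some cost in closeness of match.
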